### 2.2.2. Clinical experience with Betalutin

# 2.2.2.1. Phase 1/2 single, ascending dose study in patients with relapsed indolent NHL (LYMRIT-37-01)

This first-in-human study was performed to evaluate the safety, preliminary efficacy, PK and biodistribution of Betalutin in patients with relapsed iNHL (subtypes mantle cell, follicular grade I-IIIa, marginal zone, small lymphocytic, lymphoplasmacytic lymphoma). Patients were enrolled into 4 dose escalation arms of 3 patients each to receive a single i.v. dose of Betalutin (10, 15, 20 MBq/kg) following pre-treatment with RTX (1 or 2 doses at least 2 weeks prior), and immediate pre-dosing with lilotomab 40 mg (Arm 1) or 100 mg/m² (Arm 4), RTX (Arm 3) or no pre-dose (Arm 2) to define the MTD of Betalutin, and to collect additional PK data (n=3; Arm 5). The Phase 1 part of the study utilises a 3+3 dose-escalation study design with the primary objective of defining the MTD of Betalutin. Secondary objectives are to identify a recommended dose of Betalutin for the Phase II part of the study, and investigate the safety, biodistribution, PK and efficacy of Betalutin.

As of 03 July 2017, 62 patients have been enrolled in the study. NHL subtypes were FL (n=47 76%), mantle cell lymphoma (MCL) (n=7; 11%), and marginal zone lymphoma (MZL) (n=8; 13%). The median age of the patients was 69; 46 patients (74%) were ≥65 years old. The median number of prior therapies was 3 (range 1-8); 42 patients (68%) received ≥2 prior therapies, and 34 patients (55%) received ≥2 prior RTX courses.

Three patients were enrolled in Arm 2; the dose-limiting toxicity (DLT) rate exceeded 20% with a Betalutin dose of 15 MBq/kg, and this arm was closed. Three patients were enrolled in Arm 3 and received 15 MBq/kg Betalutin; one developed a DLT. Arm 3 was closed following a review of the first 3 patients as RTX pre-dosing on Day 0 was observed to have a lesser protective effect on neutropenia/thrombocytopenia development than either 40 mg or  $100 \text{mg/m}^2$  of lilotomab.

With a lilotomab pre-dose of 40 mg (Arm 1), the recommended dose of Betalutin for phase 2 expansion was 15 MBq/kg. In total, 36 patients have received this regimen (25 with FL); the overall response rate (ORR) is 64% (CR 25%), and 72% (CR 24%) for the FL subset, and the toxicity profile is favourable. The incidence of grade 3/4 neutropenia and thrombocytopenia was 20/36 (56%) for both. Grade 4 neutropenia and thrombocytopenia were reported in 7 patients (19%) and 6 patients (17%) respectively. Of these, there were 2 patients with grade 4 neutropenia lasting >7 days, and 2 with grade 4 thrombocytopenia >7 days.

In Arm 4 (lilotomab pre-dose of 100 mg/m²), the recommended Betalutin dose for phase 2 expansion was 20 MBq/kg. Eight patients have been enrolled; the ORR is 50%. Two FL patients have had a CR. The incidences of grade 3/4 neutropenia and thrombocytopenia were 3/8 (38%) and 4/8 (50%) respectively (there was one grade 4 thrombocytopenia reported). One patient had a DLT of haematuria with thrombocytopenia (platelet count of 40 x 10^9/L) and received a platelet transfusion. A phase 2 expansion cohort is currently enrolling up to 15 patients.

Overall, Betalutin treatment was well-tolerated, with the most common adverse events (AEs) reported being neutropenia and thrombocytopenia which were transient and generally required no intervention. Bruising/bleeding episodes were reported in 3 and 4 patients respectively; only 2 patients required platelet transfusions for bleeding events in association with thrombocytopenia (one with epistaxis and one with haematuria). Overall, 23 patients (39%) developed infections, with urinary and respiratory tract infections (including nasopharyngitis) being most commonly reported (19 patients [32%]). The majority of infections were low grade in nature. The dosing regimen was generally well tolerated, with only 2 infusion reactions reported; both were related to RTX.

Serious adverse events (SAEs) were reported in 14 patients (23%). Treatment-emergent SAEs occurring in 2 or more patients were thrombocytopenia (n=2), atrial fibrillation (n=2), sepsis (n=2) and lymphoma progression (n=2). Both atrial fibrillation episodes were grade 2 in nature and resolved within 24 hours with oral therapy. One episode was reported 9 months after Betalutin administration. Two patients were reported with sepsis; both episodes occurred in association with neutropenia around Day 40, and both fully resolved within 7-10 days with antibiotic therapy. One patient had an antecedent urinary tract infection. An SAE of myelodysplastic syndrome (MDS)/ Acute myeloid leukaemia (AML) was reported in one patient 24 months after Betalutin administration. This patient had a history of prior alkylating exposure and went on to receive 6 courses of bendamustine/RTX following Betalutin administration. MDS/AML was reported 18 months later; the outcome was fatal, and the SAE was judged to be possibly related to Betalutin and/or prior therapy by the Investigator. There was one on-study death (i.e. within 12 weeks of Betalutin administration) due to disease progression that was not considered related to Betalutin.

The PK profile of Betalutin as assessed by measuring the total radioactivity in blood shows an impact of pre-dosing with lilotomab (40 mg and 100 mg/m²), with lilotomab increasing the activity-adjusted area under the curve (AUC), and reducing the volume of distribution and rate of clearance of Betalutin, while having little effect on activity-adjusted maximum plasma drug concentration (Cmax) compared to no lilotomab pre-dosing. These observations could be consistent with blocking of the CD37 antigen sink in the bone marrow by lilotomab and consequently a reduced absorbed radiation dose compared to Arm 2. Preliminary biodistribution data (dosimetry) also indicate that both the 40 mg and the 100 mg/m² lilotomab pre-dosing regimens of Arms 1 and 4 protect the bone marrow as compared with no pre-dosing in Arm 2, since the absorbed radiation doses to red marrow are lower for Arm 1 and 4 than for

Arm 2. The maximum absorbed radiation dose to the red marrow for all patients in Arms 1 and 4 is below the previously published radiological tolerance limit (3 Gy).

For more details, please refer to the Investigator's Brochure.

[figure not shown]
### 2.3. Overview of combination treatment with Betalutin plus rituximab

[figure not shown]
### **2.3.1.** Non-clinical experience

In vitro models of Burkitt's (Ramos cells) and mantle cell lymphoma (Rec-1 cells) demonstrated increased surface CD20 expression following Lu-HH1 (Betalutin) treatment compared with cells treated with unlabelled HH1 (lilotomab) [12]. Treatment of nude mice with Ramos xenografts with Betalutin resulted in a 3-fold higher uptake of radiolabelled RTX in tumour xenografts 5 days after start of treatment than in mice treated with unlabelled HH1 (p <0.05). In SCID mice with i.v. injected Rec-1 cells, the combination of Betalutin and RTX resulted in significantly improved survival as compared with saline (NaCl) or RTX alone [12].

The therapeutic effect of the combination of Betalutin and rituximab was also studied in nude mice with s.c. Burkitt's lymphoma (Daudi) xenografts [11]. Sequential therapy with Betalutin followed by RTX substantially reduced tumour growth and improved overall survival compared to either agent alone, suggesting synergism between the 2 agents (Figure 2-1).

Figure 2-1 The effect of combining Betalutin plus RTX on tumour volume and survival in a preclinical NHL model

### 2.3.2. Clinical experience

There are no clinical data or ongoing studies combining Betalutin with RTX. One phase 2 study has been reported combining Zevalin with RTX in FL patients (summarised in Section 2.3.3).

### 2.3.3. Potential for overlapping toxicities between Betalutin and rituximab

Although there have been no prior combination studies with Betalutin and RTX, there is one report of a phase 2 study in treatment-naïve FL patients exploring short course CHOP-RTX followed at haematologic count recovery by Y-ibritumomab tiuxetan (Zevalin) and 4-weekly RTX doses (375 mg/m²), starting within 1-2 weeks of receiving radioimmunotherapy (RIT) [17]. For the 55 (out of 60) patients who completed all 3 therapies per protocol, the most frequent toxicities reported following RIT/RTX were grade 3/4 neutropenia and thrombocytopenia in 51% and 44% (grade 4 for both in 20%) of patients respectively, one prolonged episode of grade 3 serum sickness-like toxicity, and one episode of febrile neutropenia. All patients had normal white blood cell and platelet counts by Week 12 post-RIT.

The main toxicities of RTX reported in NHL patients are infusion reactions, fever, lymphopenia, chills, infection and asthenia (MabThera-prescribing information). In patients with NHL receiving RTX monotherapy, grade 3 and 4 cytopenias were reported in 48% of patients. These included lymphopenia (40%), neutropenia (6%), leukopenia (4%), anaemia (3%) and thrombocytopenia (2%). Grade 3/4 lymphopenia has been reported in approximately 30% of patients receiving Betalutin. Therefore, while combining RTX with Betalutin is not expected to contribute significantly to the development of neutropenia, thrombocytopenia or anaemia, prolonged lymphopenia may increase the incidence of infection. Patients will be monitored frequently by clinical and laboratory assessments for sequelae of myelosuppression (infections, bruising and bleeding, febrile neutropenia).

### 2.4. Benefit/Risk Assessment

Patients to be included in this study are adults with relapsed, refractory (not anti-CD20 antibody refractory) FL. The patient will have received and be considered to have experienced treatment failures from prior treatment regimens, including chemotherapy and immunotherapy treatment regimens. Treatment options for patients with relapsed/refractory FL are dependent upon the prior regimens that the patient received, and whether the patient is elderly or able to tolerate chemotherapy (due to presence of comorbidities). Generally, chemoimmunotherapy + rituximab maintenance therapy is recommended per ESMO Clinical Practice Guidelines for relapsed FL [29] For example, if a patient received prior chemoimmunotherapy with CHOPrituximab (CHOP-R) previously, then bendamustine-rituximab (BR) may be tried, or vice versa. Another option, particularly for elderly patients with comorbidities prohibiting chemotherapy, is rituximab monotherapy, however this is associated with an ORR of approximately 50% and a median time to progression of around 7-10 months [30, 31]. Radioimmunotherapy is another option but is underused. The safety profile of Betalutin is well-characterised. The most common grade 3/4 toxicities for Betalutin are thrombocytopenia and neutropenia which resolve by 3 months for the majority of patients. The incidence of bruising/bleeding episodes (7 patients), which were mostly mild in nature, and grade 3/4 infections (5 patients) was low. Infections occurred in association with neutropenia. Lilotomab pre-dosing was shown to mitigate the severity of cytopenia; evaluation of efficacy with a higher lilotomab pre-dose is on-going.

Betalutin has demonstrated clinical activity as a single agent and preliminary evidence of durable responses and is well-tolerated in patients with relapsed/refractory iNHL and FL. Preliminary efficacy data show an ORR of at least 70% for FL patients pre-treated with 40 mg lilotomab followed by 15 MBq/kg of Betalutin (Arm 1), which is the dosing regimen to be used in this study. Eighty-four per cent of patients in the LYMRIT 37-01 study have experienced some degree of decrease in tumour size [4]. Early duration of response data from Arm 1 (n=28) also suggests clinical benefit with a median duration of response of over 12 months. These are promising results in a population of primarily older, heavily pre-treated relapsed iNHL patients with advanced-stage disease.

Patients will be closely monitored for evidence of any overlapping toxicities due to combining Betalutin with RTX, such as infections, febrile neutropenia, bruising or bleeding episodes.

Taken together, the data provided demonstrate a positive benefit:risk balance for Betalutin for the treatment of patients with recurrent FL, a primarily elderly population with a high unmet medical need.

# 3. Objectives and Endpoints

Objectives and related endpoints are described in Table 3-1 below.

Table 3-1 Study objectives and endpoints

Objectives	Endpoints				
Primary					
To evaluate the safety and tolerability of Betalutin in combination with RTX	• Frequency and severity of adverse events (AEs), serious adverse events (SAEs) and changes in laboratory values graded according to CTCAE version 4.03				
Secondary					
To establish a recommended dose of Betalutin in combination with RTX for phase 2 studies in NHL patients	Frequency and severity of AEs, SAEs and changes in laboratory values graded according to CTCAE version 4.03				
To evaluate the preliminary anti-tumour activity of combination treatment based on Investigator assessment of tumour response rates	• Responses (overall response rate [ORR], complete response [CR], partial response [PR], stable disease [SD], progressive disease [PD]) per Cheson 2014 [30]				
To evaluate the duration of tumour control in	Duration of response (DoR)				
patients receiving Betalutin in combination	Progression free survival (PFS)				
with RTX	• Time to progression (TTP)				
	Overall survival (OS)				
To investigate the immunogenicity of Betalutin in combination with RTX	Monitoring of the anti-drug antibodies (ADA) response towards lilotomab, Betalutin and/or RTX				
Exploratory					
To characterise the pharmacokinetics (PK) of Betalutin in combination with RTX	Estimation of the levels of remnant administered radioactivity in blood over time (Betalutin PK)				
To assess the pharmacodynamic effects of Betalutin in combination with RTX	
 
Change from baseline in peripheral blood B-cell, T-cell and NK cell counts, tumour CD20 and CD37 expression
 
Biomarker assessments
 
				
To investigate the biodistribution of Betalutin in combination with RTX	• Estimation of whole-body retention of radioactivity at each imaging time post-injection.				
	• Estimation of the individual organ uptake/retention of radioactivity at each imaging time-point after injection.				
	Calculation of estimated absorbed radiation dose to target organ.				
To evaluate minimal residual disease in patients with a CR	Monitoring of detectable disease to assess early treatment response and detect relapse using next generation sequencing (NGS) (molecular Minimal Residual Disease (MRD))				

CONFIDENTIAL

•	To evaluate the relationship between anti- tumour activity and NHL-related genes in tumour samples	•	Gene expression analysis using a panel of cancer- related genes
•	To assess anti-tumour T-cell responses	•	Anti-tumour response measured by flow cytometry after co-culture of peripheral mononuclear cells and autologous lymphoma cells and other biomarkers

### 4. Study Design

## 4.1. Overall Design

This protocol describes a Phase 1b open-label, single-arm, dose escalation study to investigate the activity and safety and preliminary efficacy of Betalutin combined with RTX in patients with FL who have received one or more prior therapies. It is planned that 6-12 evaluable patients will be enrolled in the study.

All patients will receive a single i.v. dose of RTX (375 mg/m^2) on Day -14, and then sequential i.v. administrations of lilotomab (40 mg) followed by Betalutin (10 or 15 MBq/kg) within 4 hours on Day 0. Patients will then be administered RTX (375 mg/m^2) i.v. on Days 7, 14, 21 and 28.

Patients will undergo clinical and laboratory assessments during screening/baseline and periodically during treatment as outlined in the Schedule of activities (Section 1.2). Two cohorts of 3-6 patients will be initially evaluated for DLT, in a 3+3 escalation pattern, before determining the subsequent Betalutin dose for the remainder of the study (Section 6.1).

Tumour-tissue biopsies and blood samples will be collected to study the mechanisms of tumour response to therapy as described in the biomarkers section (Section 9.4). The collection of these samples is optional and, at Radium Hospital (Oslo, Norway) only.

[figure not shown]
PET/CT and CT imaging (or MRI) will be performed at baseline and then at 3 and 6 months. CT with contrast (or MRI) will be performed at 12, 18, 24 months or until disease progression or withdrawal from the study for any other reason (whichever comes first).

Patients who achieve SD, CR or PR on their Month 3 imaging scan will be administered maintenance RTX 375 mg/m^2 i.v. or 1400 mg s.c. every 3 months for up to 2 years (8 infusions in total), or until disease progression or withdrawal from the study for any other reason (whichever comes first).

The schedule plan for dosing and imaging is illustrated in Figure 4-1.

Study Number: LYMRIT-37-07 Version 4.0 04 Oct 2021

Figure 4-1 Study dosing and imaging plan

## 4.2. Rationale for Study Design

This phase 1b exploratory study will investigate the dosing of Betalutin in combination with RTX, whereby RTX is given 7 days following Betalutin to capitalise on potential enhanced CD20 expression following Betalutin administration. Repeat RTX doses (4-weekly, i.v.) have been safely administered to 55 treatment-naïve FL patients 1-2 weeks after 3 courses of CHOP-RTX followed by Zevalin once hematologic recovery was attained in a phase 2 study. [17]. All patients had full hematologic count recovery by 12 weeks post-RIT.

As summarised in Section 2.1, both Betalutin and RTX deplete B-lymphocytes and B-cell NHL cells. Grade 3 or higher myelosuppression (anaemia, neutropenia and thrombocytopenia) has been reported in ≤6% of NHL patients receiving RTX (MabThera prescribing information). Thus, it is anticipated that dosing RTX one week following Betalutin will not impact the development of myelosuppression acutely, although there is potential for prolonged B-lymphocyte depletion. Therefore, all patients will be closely followed clinically and with laboratory tests to monitor for infection. We hypothesise that combining Betalutin with RTX could enhance both the response rates and the durability of responses in patients with recurrent FL, providing an alternative to a chemotherapy-containing regimen for patients.

Patients with relapsed/refractory FL are reported to benefit from rituximab maintenance therapy, with improved overall survival [31]. Therefore, responding patients (i.e. those having a CR, PR or SD response following Betalutin and the 4-weekly doses of i.v. RTX) will receive maintenance RTX every 3 months for up to 2 years (a total of 8 doses), or until disease progression, commencing at Week 14. This may be administered by either i.v. (375 mg/m²) or s.c. (fixed dose of 1400 mg) routes.

The safety of patients in this study will be monitored as described in Section 9.2 (Safety Assessments). Two cohorts of 3-6 patients will be initially evaluated for DLT before determining the subsequent Betalutin dose for the remainder of the study (see Section 6.1).

### 4.3. Rationale for Dose

This is the first study evaluating the combination of Betalutin and RTX. The starting dose of Betalutin (10 MBq/kg) following a lilotomab pre-dose of 40 mg is one dose level lower than the recommended phase 2 dose for expansion (15 MBq/kg) in the LYMRIT 37-01 study and has been safely administered to 3 NHL patients. This starting dose for Betalutin is chosen to reduce the risk for overlapping toxicities, and for subsequent patients, the Betalutin dosing regimen chosen (40 mg lilotomab pre-dose and 15 MBq/kg Betalutin) has been administered to 36 patients in the LYMRIT 37-01 study, and has been well-tolerated (see Section 2.2.2.1). As of the writing of this protocol, 11 patients (evaluable for safety) have received a lilotomab pre-dose of 100 mg/m² followed by 20 MBq/kg Betalutin, therefore the clinical profile of the former regimen is better characterised.

Regarding immunogenicity, the presence of anti-drug antibodies (ADA) was reported for 7 out of 62 patients enrolled. The observed ADA response was transitory, detected after 7 days (n=1) or 1 month (n=6). For one of the two patients with 12-months post-treatment results available, a new onset of ADA was observed. Two patients who were treated with a lilotomab pre-dose of 100 mg/m² developed ADAs at 1 month that disappeared by 3 months. None of the patients treated with 40 mg lilotomab and 15 MBq/kg Betalutin developed ADAs.

The dose regimen of RTX chosen is that which had been approved for use in relapsed/refractory FL patients. RTX has single agent activity in relapsed FL and has been safely combined using both single and multiple doses with a number of myelosuppressive chemotherapeutic agents and regimens including bendamustine, CHOP (cyclophosphamide, doxorubicin, vincristine, prednisone) and CVP (cyclophosphamide, vincristine, prednisone) as standard therapy for NHL patients. In contrast to standard chemotherapy, side effects of RTX are modest (mostly chills, fevers, headache and infusion reactions) and mainly confined to the first infusion of rituximab. In combination with CHOP and CVP, the incidence of grade 3 or 4 neutropenia is approximately 10% higher than with CVP or CHOP alone, without a difference in overall infection rate or sepsis [24, 33].

As discussed in the previous section, as patients with relapsed/refractory FL are reported to benefit from rituximab maintenance therapy [31], responding patients (i.e. those having a CR, PR or SD response following Betalutin and the 4-weekly doses of i.v. RTX) will receive maintenance RTX every 3 months for up to 2 years (a total of 8 doses), or until disease progression or withdrawal from the study for any other reason (whichever comes first), commencing at Week 14.

# 4.4. Patient and Study Completion

Approximately 10-15 patients will be screened to achieve 6-12 patients assigned to study treatment and evaluable.

# 4.5. End of Study Definition

The end of study for all patients will be the date of the last patient last visit upon completion of their end of study visit(25 months after receiving their Betalutin treatment if ending study treatment per protocol, or after disease progression or withdrawal from the study for any other reason, (whichever comes first) or if the study is terminated early.

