	Two cohorts of 3-6 patients will be initially evaluated for dose limiting toxicity before determining the subsequent Betalutin dose for the remainder of the study. Dose-escalation decisions will be made by the Investigator(s) and Sponsor following review of the safety data once haematologic recovery has occurred.
	After the last dose of rituximab, vital signs, ECG (final visit only), physical examination, haematology, serum biochemistry, Adverse Drug Reaction (ADR) and Adverse Events of Special Interest (AESI) will be collected at an end of study visit that will occur at least 28 days post last administration of study treatment. Patients in survival follow-up at time of Protocol v4.0 approval can have the EOS visit at their next scheduled visit or an earlier convenient time point.
Pharmacokinetics and biodistribution	Total radioactivity measurements in blood will be performed at certain intervals until Day 28. Mandatory at Radium Hospital (Oslo, Norway) only, otherwise optional. Patients will undergo SPECT imaging at certain time points in order to measure distribution of

	Betalutin in the body and calculate absorbed radiation dose to target organs/tissues and tumours.
Biomarker assessments	Biomarkers assessments including CD20 and CD37 expression in tumour tissue biopsy and immunophenotyping of circulating lymphocyte subsets (absolute cell counts), will be performed at various time points throughout the study
Other biomarker studies on additional samples	Biomarkers including but not exclusive to MRD (blood) and gene expression changes related to disease treatment in tumour tissue (archival or newly collected biopsy at screening, relapse or disease progression), will be assessed at various time points throughout the study. Patient's major histocompatibility complex (MHC) class I/II haplotype will be defined using peripheral blood (DNA) or saliva (DNA). Anti-tumour T-cell responses will be explored by flow cytometry after co-culture of peripheral mononuclear cells (blood) and autologous lymphoma cells (biopsy and/or needle aspirate), and other biomarkers at selected time points throughout the study at Radium Hospital (Oslo, Norway) only.
Statistical methods and data analysis	The safety analysis population will include all patients who received at least one dose of any study drug.

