	The intent-to-treat (ITT) population will consist of all patients who were enrolled and treated with lilotomab/Betalutin, regardless if RTX therapy was initiated. The number and percentage of patients with each response and overall (complete + partial responders) will be presented for each time point for the ITT population.
	Pharmacokinetic, biodistribution and biomarker exploratory analyses will be described in the statistical analysis plan finalised before database lock.
Key dates	The start date of the study (first patient included) was in October 2018.
	The expected accrual time is 18 months.
	Patients will be followed up for up to 25 months (End of study visit) after Betalutin administration.
	Patients in survival follow at time of Protocol version 4.0 approval can have the EOS visit at their next scheduled visit or an earlier convenient time point

CONFIDENTIAL

Protocol Study Number: LYMRIT-37-07

Version 4.0\_04 Oct 2021

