## 7. Discontinuation of Study Treatment and Patient Withdrawal / Discontinuation

## 7.1. Discontinuation of Study Treatment

The study may be discontinued at the discretion of the investigator or Sponsor in the event of the following:

- Occurrence of serious adverse reactions, including abnormalities in laboratory analysis and vital signs which by virtue of their nature, severity and duration are considered evidence that the safety of the study patients is no longer assured
- Medical or ethical reasons affecting the continued performance of the study
- Difficulties in the recruitment of patients
- Cancellation of drug development

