## 7.2. Patient Withdrawal/Discontinuation from the Study

In accordance with the Declaration of Helsinki, each patient is free to withdraw from the study at any time. Investigator(s) also have the right to withdraw patients from the study in the event of illness, AEs, or other reasons concerning the health or well-being of the patient, or in the case of lack of cooperation.

Should a patient decide to withdraw after administration of the study drug(s) or should the Investigator(s) decide to withdraw the patient, all efforts will be made to complete and report the observations up to the time of withdrawal as thoroughly as possible. A complete final evaluation at the time of the patient's withdrawal (end of study visit) should be made within 28 days (± 3 days) of receiving the last study treatment administration if ending treatment per protocol, or within 7 days of taking the decision to withdraw if it occurs > 28 days after the last study treatment administration and an explanation given of why the patient is withdrawing or being withdrawn from the study. The reason and date for withdrawal must be noted in the eCRF. If the reason for withdrawal is a clinical AE or an abnormal laboratory test result, monitoring will continue until the outcome is evident. The specific event or test result(s) must be recorded in the eCRF. If the reason for withdrawal is due to disease progression, the study site should make all effort to continue with the safety monitoring.

Haematological toxicity was observed in the phase 1/2 LYMRIT-37-01 study, with nadir values 5 to 7 weeks after injection of Betalutin. It is advisable to monitor the haematology parameters of the withdrawn patients between 6 and 9 weeks after the last RTX administration or until recovery to CTCAE grade 1 or less.

Single patient study discontinuation is per definition, when the patient:

- has completed Month 24 administration of rituximab, per protocol or
- experiences one of the following situations before per protocol end of study:
  - withdraws consent to participate in the study
  - has died
  - is lost to follow up
  - has disease progression
  - starts further anticancer therapy or
- when the patient is withdrawn for a reason other than described above

CONFIDENTIAL

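### The protocol does not separate stopping rituximab from leaving the study, so a patient who stops without progression may lose scans and be scored as PD without one

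*Combined protocol and SAP*

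**What the plan says.** **End of follow-up.** Section 4.5 places it at "25 months after receiving their Betalutin treatment if ending study treatment per protocol", or after progression or withdrawal. The synopsis (Key dates) has no treatment condition: "Patients will be followed up for up to 25 months (End of study visit) after Betalutin administration". Section 7.2 opens its list of ways a patient ends the study with "has completed Month 24 administration of rituximab, per protocol or". It then names withdrawn consent, death, loss to follow-up, progression and new anticancer therapy, and closes with an open category: "when the patient is withdrawn for a reason other than described above".

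**Stopping treatment.** Section 7.1 is titled Discontinuation of Study Treatment, but its text begins "The study may be discontinued at the discretion of the investigator or Sponsor in the event of the following" and lists only grounds for ending the trial. For an adverse event in one patient, Section 7.2 says "Investigator(s) also have the right to withdraw patients from the study in the event of illness, AEs, or other reasons". Sections 4.1 and 4.3 end maintenance at eight doses, progression or study withdrawal. Section 7.2 also sends the reader to the Schedule of Activities for what to collect when treatment is discontinued, but Tables 1-1 and 1-2 have no such visit.

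**Scans and final visit.** Section 4.1: "CT with contrast (or MRI) will be performed at 12, 18, 24 months or until disease progression or withdrawal from the study for any other" cause. The synopsis (Safety assessments) says that final safety data "will be collected at an end of study visit that will occur at least 28 days post last administration of study treatment". Section 8.2.19 provides for two groups only: per-protocol completers, and patients who leave the study before Month 24.

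**Analysis.** Section 10.1 counts withdrawn patients as PD at all visits after withdrawal. It names DoR, PFS, TTP and OS but gives no event or censoring rule for them.

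**The concern.** These sections recognise two states: completing treatment per protocol, or leaving the study. A patient in CR, PR or SD who stops maintenance for an adverse event fits neither unless someone withdraws them. One site could withdraw the patient and another could keep scanning, and both could defend the choice from the text.

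Two things are at stake. First, a scan not done cannot be recovered at analysis. Patients who stop rituximab for toxicity may also differ in outcome from those who continue, so the missing scans could be informative. Second, the withdrawal rule and the PD rule act together: a patient in documented CR who is withdrawn after stopping rituximab would be tabulated as PD with no scan showing it. That is a wrong response status, not merely a missing one, and in a study of 6 to 12 patients a single case is visible.

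**Working it through.** **1. The plan's own timing.** Table 1-2 gives maintenance at Weeks 14, 26, 39, 52, 65, 78, 91 and 104, which is 8 doses. Section 8.2.19 puts the per-protocol end of study visit 28 days after the last one: 104 + 28/7 = Week 108. In months, 108 × 7 / 30.4375 = 24.8, which agrees with the stated Month 25. So the 25 months are exactly the last rituximab dose plus four weeks.

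**2. Scans lost if a stop is handled as withdrawal.** Post-baseline scans fall at Weeks 12, 26, 52, 78 and 104 (Months 3, 6, 12, 18 and 24). Assume exit at last dose + 4 weeks, and count the scans that fall later.

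| Last dose (week) | Exit week | Last scan | Scans lost of 5 |
|---|---|---|---|
| 1 (14) | 18 | Month 3 | 4 |
| 2 (26) | 30 | Month 6 | 3 |
| 3 (39) | 43 | Month 6 | 3 |
| 4 (52) | 56 | Month 12 | 2 |
| 5 (65) | 69 | Month 12 | 2 |
| 6 (78) | 82 | Month 18 | 1 |
| 7 (91) | 95 | Month 18 | 1 |
| 8 (104) | 108 | Month 24 | 0 |

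Section 8.2.19 also allows a withdrawal decision later than 28 days after the last dose. If the decision falls at the next dosing visit and that visit's scan is still done, the losses after doses 1 to 7 become 3, 3, 2, 2, 1, 1 and 0.

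If the patient stays on study, all 5 scans are kept whatever the last dose.

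**3. Effect on a visit's response rate.** One responder recoded as PD moves the CR + PR percentage by 100/n: 100/12 = 8.3 points, or 100/6 = 16.7 points. This applies at each visit after withdrawal. A patient in SD would move between the SD and PD rows and leave CR + PR unchanged.

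**4. How likely is at least one such patient?** The documents give no rate of stopping maintenance, so this is purely an assumption. With stop probability q, the chance of at least one among n patients is 1 − (1 − q)^n.

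- q = 5%: 1 − 0.95^6 = 26% and 1 − 0.95^12 = 46%.
- q = 30%: 1 − 0.70^6 = 88% and 1 − 0.70^12 = 99%.

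**5. DoR, PFS and TTP.** If withdrawal truncates follow-up, observed progression events can only fall. If the PD rule of Section 10.1 carries over, each withdrawal becomes an event and the count can rise. The plan does not choose, so not even the direction of the effect can be stated.

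**The case against.** The strongest reply is that no rule makes a rituximab stop an exit. Imaging ends at progression or withdrawal from the study, never at the last dose (Sections 4.1 and 9.1.2). Stopping rituximab is not among the named grounds in Section 7.2, and the investigator's power to withdraw a patient for an adverse event is permissive. The synopsis timing of at least 28 days after last treatment is a minimum, so a Month 25 visit after an early stop would satisfy it. Read literally, the patient stays on the scan schedule unless somebody withdraws them.

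This stands, and it limits the point. A reader might infer that stopping rituximab means losing the remaining scans, or that DoR, PFS and TTP are cut off at treatment stop. The first is not a stated rule; the second is contained nowhere in the plan. A reader might also see a conflict with the ITT definition in Section 10.1.1, but that definition settles who is analysed, not how long they are followed.

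The reply does not remove the gap. Section 7.2 ends with an open category, per-protocol completion requires the Month 24 dose, and no passage tells a site to continue scans after a stop.

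It is also fair to say that the primary endpoint is safety, and that no test or sample size depends on the duration endpoints.

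**Conclusion.** The point holds as a gap that should be closed: the protocol does not distinguish stopping study treatment from leaving the study, and its analysis rule can then assign PD without evidence. Its size is conditional. If a stop without progression is handled as withdrawal with exit four weeks after the last dose, 1 to 4 of 5 scans are lost for a last dose of 7 down to 1. A responder so handled moves each later visit's response rate by 8.3 to 16.7 points. A later withdrawal decision can reduce the loss by one scan.

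No expected number of affected patients, and no percentage change in progression events, can be derived from the documents. Both need a stop rate, and the second also needs a censoring rule. The affected endpoints are secondary and descriptive, so this bears on the accuracy of the response and duration summaries, not on any formal decision.

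**What to change.** Reconcile Sections 4.5, 7.1, 7.2 and 8.2.19 so that stopping study treatment and leaving the study are separate events. A patient who stops rituximab without progression, new anticancer therapy or withdrawal of consent stays on study, has the scans and visits already in Table 1-2 to Month 24, and has the end of study visit at Month 25. Give Section 7.1 text that matches its title, and make the Section 7.2 pointer to the Schedule of Activities lead to an actual entry.

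In Section 10.1, state that stopping rituximab alone is neither counted as PD nor a censoring point for DoR, PFS and TTP.

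The cost is amendment wording plus a few site visits and scans for patients who are off treatment. No new type of procedure is added. The change does not address when rituximab should be stopped.
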